	13.1 Authorship policy	
	13.2 Publication	
	13.3 Peer review	
14	REFERENCES	27

Protocol Development

Chief Investigator, [name]: Initial draft, review and final approval

Co-Investigator, [name]: Review

Co-investigator, [name]: Review

Co-Investigator, [name]: Review

Co-Investigator, [name]: Review

Co-Investigator, [name]: Review

Co-Investigator, [name]: Review

Co-Investigator, [name]: Review

Co-Investigator, [name]: Review

Co-investigator, [name]: Review

Co-investigator, [name]: Review

Co-investigator, [name]: Review

Co-investigator, [name]: Review

Study Manager, [name]: Review

Senior Research Statistician, [name]: Review

STUDY SUMMARY/SYNOPSIS

Study Title	FOcused LongitudinaL Observational study to improve knoWledge of COVID-19
Study Design	Prospective observational cohort
Study Population	Individuals previously diagnosed with COVID-19 disease, including a subset with severe ARDS
Sample Size	300
Planned study period	6 years
Clinical phase duration	6 months
Follow up phase duration	Up to 25 years

Primary	Objectives	Outcome Measures	
	To describe the consequences of	From 3-6 months post-COVID-	
	COVID-19, on the airway	19, describe the early	
	epithelial microbiome, and on	longitudinal changes in the	
	longitudinal lung epithelial and	airway epithelial microbiome and	
	vascular function, in a cohort of	mycobiome	
	patients who have had a spectrum		
	of disease as a result of infection		
	with SARS-CoV2.	A detailed description of the	
		early (3-6 months) regenerating	
		ultrastructural changes in the	
		nasal airway epithelium, using a	
		combination of video	
		microscopy, electron	
		microscopy, and cell culture	
		techniques, in a spectrum of	
		patients recovering from COVID-	
		19.	
		Using non-invasive techniques,	
		perform assessments of	
		microvascular and	
		macrovascular endothelial	
		function, arterial stiffness, and	
		vascular inflammation, in the 3-6	
		months following severe and	
		non-severe COVID-19; these	
		can be linked to inflammatory	
		intravascular gene expression in	
		PBMCs and whole blood.	

Secondary	Objectives	Outcome Measures	
	Describe neutrophil function in survivors of severe COVID-19 pneumonia.	To characterise neutrophil function in survivors of severe COVID-19 pneumonia, including those who had ARDS, and link to clinical phenotypes.	
	To generate a biobank of samples from patients who are recovering from COVID-19, which can later be used to identify and predict recovery from severe COVID-19 across a range of health domains, including diabetes. To determine long term healthcare resource utilisation in patients who have had COVID-19 disease.	To characterise the effect of COVID-19 on complications and management of diabetes, using the SCI-diabetes database and look for the underlying associated biomarkers relating to metabolic function (such as adipokines) that might be associated with differential outcomes. Long-term assessment of healthcare utilisation using electronically linked health care records, and phone interviews, and linking these outcomes with the work streams described above, and with biomarker discovery from stored samples.	
Inclusion Criteria:	Previous clinical (only if hospitalised) or microbiological (if hospitalised		
	or non-hospitalised) diagnosis of COVID-19 disease.		
	Age > 18 years (no upper age limit)		
Exclusion criteria:	Unable to give informed consent.		
	Participation is not in the interests of the patient as determined by the investigator (e.g. palliative care).		

If an individual has any symptoms compatible with current COVID-19
(as per the Health Protection Scotland Guidelines relevant at that
time).
If an individual is currently isolated following a contact with COVID-19.
If an individual has had an upper respiratory tract infection in the
preceding 14 days.
Nasal brushings only: Patient has a history of significant epistaxis or
is anti-coagulated.

1 BACKGROUND AND RATIONALE

Coronaviruses (CoVs) are positive-sense single stranded enveloped RNA viruses, many of which are commonly found in humans and cause mild symptoms. Over the past two decades, emerging pathogenic CoVs capable of causing life-threatening disease in humans and animals have been identified, namely Severe Acute Respiratory Syndrome coronavirus (SARS-CoV) and Middle Eastern Respiratory Syndrome coronavirus (MERS-CoV).

In December 2019, the Wuhan Municipal Health Committee (Wuhan, China) identified an outbreak of viral pneumonia cases of unknown cause. Coronavirus RNA was quickly identified in some of these patients. This novel coronavirus has been abbreviated as SARS-COV-2 and the disease caused by this virus has been designated COVID-19. The disease has now spread to affect millions of patients worldwide with widespread community transmission across the globe.

Mortality from COVID-19 has been estimated at 0.66% of infected patients¹ and occurs most frequently because of the development of Acute Respiratory Distress Syndrome (ARDS). In the UK, one third of patients admitted to hospital with COVID-19 have died, and in intensive care, survival is approximately 50%, significantly worse than other viral pneumonias². In addition to ARDS, the use of renal replacement therapy in ICU is also associated with poor outcome, and general risk factors for death include Age, Male Sex, Obesity, Chronic Lung Disease, Cardiovascular Disease and Diabetes³. It is notable that risk factors that influence vascular endothelial health, such as diabetes and cardiovascular disease, have exerted a significant effect on outcome.

ARDS occurs in up to 10% of all COVID-19 cases³, while extensive pulmonary infiltrates have also been reported in patients not requiring mechanical ventilation. The pulmonary effects of SARS-CoV-2 are thought to be mediated through a combination of interstitial damage and endothelial inflammation, leading to a combination of both ventilation and perfusion defects⁴; this seems to be in contrast to changes seen in severe influenza where endothelial disease is less common⁵. Influx of neutrophils to the lung, leading to damage from host-derived proteases, is a key part in this pathogenic process.

While most patients with COVID-19 are likely to make a full recovery, previous studies in other severe coronavirus diseases such as SARS suggest that a proportion of patients, perhaps as high as 4%, will experience long term irreversible pulmonary disease⁶. Persistent respiratory symptoms and poor quality of life are also described and have already been seen in UK cohorts at an early stage (own unpublished data). Given the concerns around post-COVID-19 lung damage, longitudinal changes in lung inflammatory processes (such as those driven by or ameliorated by neutrophils) and the pulmonary microbiome post-COVID-19 may be important in shaping the outcomes of patients with structural lung disease.

The multi-site PHOSP-COVID Study (in which [name] and [name] are also Principal Investigators) will study these broad changes at scale within the UK; yet the granular detail of how these outcomes are reflected in structural and microbiological changes in the airway and in the lung also need to be examined, so that the biology of the post-COVID-19 lung can be better understood. Studying regenerative epithelial changes in the airway following COVID-19 disease, along with longitudinal changes in the airway epithelial microbiome and neutrophil function following illness, are the planned key **pulmonary/airway** work streams in FOLLOW-COVID and complement the work of PHOSP-COVID.

Given the ubiquity of the receptor for SARS-CoV2 (ACE2), the virus has the ability to affect multiple organ systems. Enhanced ketosis in patients with diabetes, strokes, myocardial infarctions, as well as gastrointestinal ischaemia have all been described as occurring following COVID-19⁷. There are also reports of a range of vascular dermatological complications including Raynaud's phenomenon. Consequentially, long term effects on other aspects of non-pulmonary health, particularly in endothelial function, cardiovascular disease, and diabetes, have also been hypothesised to follow severe COVID-19 and may compound the effects on the lung. Understanding these broader and more nuanced effects will be important given their wide-reaching effects on the nation's future health. This is particularly the case given that established risk factors noted above, such as obesity or diabetes, which make severe disease with COVID-19 more likely, may also later influence longer term cardiovascular outcome. Work in the linked areas of vascular function, metabolism and diabetes, are therefore the key **non-pulmonary** work streams in FOLLOW-COVID.

By May 2020, over 18,000 Scottish people have been found to have been infected with SARS-Cov-2, with over 2,450 deaths. Many hundreds of patients have already been treated in Intensive Care, with over 4,000 treated in hospital for COVID-19 pneumonia⁸. The long-term effects on these individuals is presumed to be significant, and future waves of disease may increase these numbers greatly. The impact on Scottish healthcare utilisation in the future may be very significant as a result. One example is that of Chronic Kidney Disease: it is not yet known how the impact of severe COVID-19 - where Acute Kidney Injury and the requirement for Renal Replacement Therapy conferred a significantly higher risk of death - will impact on future risk of CKD and if this can be predicted from early biomarker analysis.

To start to understand these challenges, this study will recruit a cohort of individuals affected by COVID-19 so that they can be studied over time in a focused and detailed series of predefined pulmonary and non-pulmonary workstreams centred around epithelial and endothelial health. These patients may also be part of the multi-site UK PHOSP-COVID study, which aims to provide a more broad-reaching overview of the short, medium, and long-term effects of hospitalisations with COVID-19, particularly around lung disease on its broadest terms. Initially, data collection will occur over 6 months in order to provide urgent focused data to help inform Scottish clinical practice with regard to post-COVID-19 health, but the cohort will be established so that the patients can be followed-up for up to 25 years, and linkage to longer term health outcomes can be explored.

2 STUDY OBJECTIVE AND OUTCOMES

Primary objectives:

• To describe the consequences of COVID-19, on the airway epithelial microbiome, and on longitudinal lung epithelial and vascular function, in a cohort of patients who have had a spectrum of disease as a result of infection with SARS-CoV2.

Secondary objectives:

- To describe neutrophil function in survivors of severe COVID-19 pneumonia.
- To generate a biobank of samples from patients who are recovering from COVID-19, which can later be used to identify and predict recovery from severe COVID-19 across a range of health domains, including diabetes.
- To determine long term healthcare resource utilisation in patients who have had COVID-19 disease.

Clinical outcomes, against which it will be possible to track changes over time, and test biomarkers, will include:

-Mortality

-Healthcare utilisation in broad terms, including that for diabetes, renal disease, cardiovascular disease and pulmonary disease.

-Symptom burden and Quality of Life

-Frequency and type of Pulmonary Infections

2.1 Objectives

The broad study objectives are to recruit and study over time a cohort of patients who have had COVID-19, particularly severe disease; understand the effect this has had on their epithelial and vascular function; and how these effects are associated with later healthcare-related clinical outcomes such as pulmonary infections, diabetic management and cardiovascular disease. Specifically:

-To characterise the microbiome of the airway epithelial surface in patients following COVID-19 lung disease within 6 months of recovery from acute illness.

-To investigate the ultrastructural and functional consequences to the airway epithelium following COVID-19 lung disease within 6 months of recovery from acute illness.

-To characterise vascular function in patients who have had severe and non-severe COVID-19 disease, stratified by presence of pre-morbid cardiovascular disease and diabetes.

-To characterise neutrophil function in survivors of severe COVID-19 pneumonia, including those who had ARDS.

-To characterise the effect of COVID-19 on complications and management of diabetes, using the SCI-diabetes database and look for the underlying associated biomarkers relating to metabolic function (such as adipokines, inflammatory markers, and hormones associated with fat metabolism) that might be associated with differential outcomes.

-To generate a biobank of samples that will allow the future testing of biomarker-led hypotheses in the prediction of healthcare utilisation and prediction of recovery from COVID-19.

2.2 Outcomes

Aim: From 3-6 months post-COVID-19, describe the early longitudinal changes in the airway epithelial microbiome and mycobiome (work here complements the microbiome components of PHOSP-COVID, which will look at sputum samples).

Aim: A detailed description of the early (3-6 months) regenerating ultrastructural changes in the nasal airway epithelium, using a combination of video microscopy, electron microscopy, and cell culture techniques, in a spectrum of patients recovering from COVID-19.

Aim: Using non-invasive techniques, perform assessments of microvascular and macrovascular endothelial function, arterial stiffness, vascular inflammation, and fat metabolites in the 3-6 months following severe and non-severe COVID-19; these can be linked to inflammatory intravascular gene expression in PBMCs and whole blood.

Aim: From 3-6 months post-COVID-19, describe neutrophil function in patients recovering from severe COVID-19 pneumonia, including those with ARDS.

Aim: Linking with the SCI-Diabetes database to obtain a comprehensive analysis of the impact of COVID-19 on diabetes care in affected patients and linking this to changes in serum metabolic biomarkers obtained 3-6 months following COVID-19.

Aim: Long-term assessment initially over 5 years and up to 25 years of healthcare utilisation using electronically linked health care records, and phone interviews, and linking these outcomes with the work streams described above, and with biomarker discovery from stored samples.

3 STUDY DESIGN and METHODS of DATA COLLECTION AND DATA ANALYSIS

3.1 Study description

This is a prospective observational study in hospitals in Scotland. Patients who have had a diagnosis of COVID-19, including those not hospitalised, will be recruited to this study following informed consent. Potential participants will be approached by a member of the treating medical team who will discuss the study with them and provide a copy of the PIS to consider. If hospitalised, this will be done towards the end of their hospital admission, or up to 6 months following discharge from hospital. Non-hospitalised patients will be approached in outpatient COVID-19 convalescence clinics, or via local virological databases. Study invitation may be by letter. Basic demographic data and medical history will be assessed from the patient and the case notes, contemporaneously and in retrospect where necessary. Details of the patient's care (including care in high dependency or intensive care) during their

acute illness and convalescence with COVID-19 will be recorded. If a hospitalised patient, they may be simultaneously recruited into another UK-based follow-up study (PHOSP-COVID) which will study a wide variety of outcomes including those relating to quality of life and lung health.

Approximately 3-6 months following discharge, or from episode of illness if not an inpatient, the patient will provide blood samples, a urine sample, and a nasal and throat swab taken for the planned microbiome studies. Patients from the NHS Tayside study site will have a nasal epithelial brush for the planned epithelial airway studies. If able, they will be asked to fast for 10 hours prior to the blood tests so that fasting blood ketones can be measured. The airway brush and swab samples will all be processed as per standardised laboratory protocols for the studies into nasal epithelial function and the airway microbiome respectively. The blood and urine samples will be processed as per laboratory protocols, with samples stored as a biobank for the endothelial and diabetes studies, as well as for future studies into healthcare utilisation.

[figure not shown]
At approximately 6-8 months, they will be invited to repeat the blood samples, urine sample, nasal brush and airway swab samples.

Between 3 and 6 months, patients from NHS Tayside - approximately 120 - will be invited to take part in detailed, non-invasive tests relating to vascular function (designated as FOLLOW-VASC within this study). Microvascular endothelial function will be assessed using iontophoresis of vasoactive chemicals and laser Doppler imaging. Assessment of macrovascular function will be performed by measuring flow-mediated dilation (FMD) of the brachial artery using an 8-15 MHz linear array ultrasound. Finally, systemic arterial stiffness will be measured using aortic pulse wave velocity and augmentation index.

There will be phone call assessments at 1 year, 2 years and 5 years following discharge from hospital. Electronic medical record linkage will be used to look at contacts with primary care and comprehensive healthcare resource utilisation during the follow-up period from 6 months onwards up to 25 years; the SCI-diabetes database will be used to extract data specifically for patients with diabetes, to assess the effect of COVID-19 on longer term diabetes control, body weight and complications within the cohort (designated FOLLOW-DIABETES within this study).

Reasonable travel expenses will be available to participants to attend study visits.

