3.2 Study flowchart

3.3 Study Assessments

	Time after discharge/episode of illness			
	Study entry	3 (to 6) months	6-8 months	1, 2 & 5 years
Informed consent	Х			
Baseline information	Х			
Blood		Х	Х	
Urine		Х	Х	
Nasal and Throat Swab		Х	Х	
Nasal brushing (NHS Tayside patients)		Х	Х	
Endothelial/Vascular Optional Investigations FOLLOW-VASC (NHS Tayside patients)		x		
Phone call assessment				X
Long term follow-up via records inc. FOLLOW- DIABETES work using SCI-Diabetes			X	X (up to 25 years)

Up to 50ml of blood will be taken at each indicated venepuncture assessment (as other studies are being conducted to which the patient may also be recruited, no more than 100ml of blood between all studies will be taken at any time point). This will be split for isolation of peripheral blood mononuclear cells (PBMCs), neutrophils, and plasma (if at NHS Tayside study site); and also serum (all study sites). At all study sites, a blood tube for gene expression analysis will also be taken and an EDTA tube for genetic analysis. Some routine blood tests for Full

[figure not shown]
Blood Count, and Urea and Electrolytes and measurement of HbA1c and serum lipids (if appropriate) will also be taken (unless already taken for clinical purposes).

Where indicated, a urine sample will be taken and dipsticked, and tested for protein content. The remainder will be stored for further analysis and sent for albumin creatinine ratio (ACR) where relevant (e.g. patients with diabetes).

A nasal and throat swab will be taken at all study sites, using an approved standard operating procedure, and safely stored at the study site until used for the sequencing/microbiome studies.

A nasal brushing will be taken from 30 patients at the NHS Tayside study site using an approved standard operating procedure. This involves removing surface cells from the mucosal lining of the nose with a small cytology brush. This will be processed using standardised laboratory protocols for cell culture and microscopy.

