3.5 Tissue

Samples of blood, urine, and nasal and throat swabs will be taken in all study recruits. These will be processed on site, safely stored in the Clinical Research Facility, and later sent to the University of Dundee respiratory research lab for analysis. A nasal brushing will be collected in individuals from the NHS Tayside study site. Any surplus tissue will be retained for future ethically approved research for up to 10 years. Samples will be stored in the University of Dundee respiratory research lab and registered with the Tayside Biorepository.

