6 DATA COLLECTION & MANAGEMENT

6.1 Data collection

Paper records (e.g. CRFs, consent forms) will be kept at the recruiting sites in a secure physical location.

Clinical data collected at visits will be recorded in a paper CRF and transferred to a password protected Excel file for ease of analysis. Associated relevant data e.g. demographics, symptoms, will also be stored electronically in Excel format. This will be pseudoanonymised and stored only with associated study identifier. No personal identifiers will be kept with medical data.

Paper CRFs will be stored in a locked filing cabinet in the clinical research facility.

CRFs will be managed in accordance with Sponsor SOP.

Data will be collected form the patient, medical notes, MDT notes, hospital clinical systems such as ICE, Clinical Portal and Ekora.

We will collect data that will include but is not limited to:

COVID Research Studies already entered

• Which studies and which meds given

Basic Individual Data

- Age
- Sex
- BMI
- Ethnicity
- Past Medical History
- Medications
- Inpatient or Outpatient
- Postcode for SIMD
- Employed/Not employed

Basic Data from Acute Admission/Readmissions

• Observations at presentation if inpatient

- Urine Dipstick if done
- Length of stay and if re-admitted
- Needed oxygen or not and how much at peak
- HDU or ICU and length of time on each
- CPAP vs HFNC vs both
- Time invasively ventilated in ICU
- Requirement for Acute/New Renal Replacement Therapy
- Other events during admissions/re-admissions: heart attack/stroke/PE etc.

Follow-up/Convalescence Data

- Symptom Questionnaires
- Clinical details of follow-up symptoms and outcomes
- Observations including ECG, urine dipstick

Blood tests/Other investigations

- Baseline, Peak, Convalescence blood tests during admission and in follow-up
- Echo if done
- CXRs at baseline and in convalescence
- Other imaging during acute illness and convalescence

SCI - Diabetes

Collects data from primary and secondary care on more than 99% of patients in Scotland with diabetes. SCI-Diabetes provides a fully integrated shared electronic patient record to support treatment of NHS Scotland patients with Diabetes. It is developed, maintained and supported by the SCI-DC Development Team, Tayside. It includes data on:

- Weight/BMI
- Blood Pressure
- Smoking, exercise & alcohol history
- Biochemistry HbA1c, creatinine, eGRF, lipids, urine albumin,
- All prescribing
- Retinal screening outcomes
- Foot screening outcomes

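### The diabetes aim is worded as an effect of COVID-19, but the protocol states neither a pre-illness SCI-Diabetes window nor an uninfected comparator

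*Protocol*

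**What the plan says.** **Aim.** Section 2.1 states the diabetes objective as "To characterise the effect of COVID-19 on complications and management of diabetes, using the SCI-diabetes database", and the synopsis repeats it. Section 2.2 promises a "comprehensive analysis of the impact of COVID-19 on diabetes care in affected patients". Section 3.1 says the register will be used "to assess the effect of COVID-19 on longer term diabetes control, body weight and complications within the cohort".

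**Population.** Section 5.1.1 admits only people with a previous diagnosis of COVID-19. No uninfected group appears anywhere in the protocol.

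**Window.** In section 3.1, linkage of general records covers primary care contacts and "comprehensive healthcare resource utilisation during the follow-up period from 6 months onwards up to 25 years". The SCI-Diabetes clause follows a semicolon and has no dates of its own. In the section 3.3 schedule, the row "Long term follow-up via records inc. FOLLOW- DIABETES work using SCI-Diabetes" is marked at 6-8 months and at 1, 2 and 5 years (up to 25 years). It is blank at study entry and at 3 to 6 months.

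**Register.** Section 6.1 says of SCI-Diabetes: "Collects data from primary and secondary care on more than 99% of patients in Scotland with diabetes". Its listed content includes HbA1c, weight, prescribing, and retinal and foot screening.

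**The concern.** An effect is a contrast with what would have happened without the illness. The protocol asks for an effect but schedules register data only after the illness, and only in people who had it. HbA1c and weight drift, complications accumulate with age and diabetes duration, and routine diabetes care may change over calendar time. All of these would be read as consequences of COVID-19.

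This is not a detail that can wait for an analysis plan. Such a plan can choose a model, but it cannot analyse data that were never requested. Section 6.2 restricts the data system to what the study aims require, section 6.1 places extraction with outside bodies, and section 12.1 requires amendments to be approved before use. A look-back or a comparator therefore needs explicit provision in the protocol.

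**Working it through.** **1. What can be estimated from the stated data.** Write a person's HbA1c at time t after illness as

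Y(t) = pre-illness level + drift(t) + calendar effect + COVID-19 effect(t).

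- All participants are infected, so the COVID-19 effect is never absent.
- All scheduled register times are after illness, so the pre-illness level is never seen alone.
- The level after illness therefore gives only the sum of the pre-illness level and the effect. The slope gives only the sum of drift, calendar change and any change in the effect.
- Raising n narrows the interval around these sums. It does not split them.

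**2. Whether other data in the protocol fill the gap.**
- Section 3.1 takes medical history from the patient and case notes, in retrospect where necessary. Section 6.1 adds medications, admissions and readmissions, and blood tests from admission and convalescence. None of this is specified as a serial pre-illness record of diabetes control.
- Section 3.3 includes HbA1c, if appropriate, at the 3 to 6 and 6-8 month blood draws. These values also come after the illness.
- Severe against non-severe disease is a possible internal contrast, but it compares severity. It does not give the effect of having had COVID-19.
- Section 2.2 links the diabetes analysis to serum biomarkers taken at 3 to 6 months, yet the schedule marks no register data in that column.

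**3. What a contrast could detect (illustration).** The protocol gives no diabetes share, SD, alpha or power, and section 7.1 says no informed power calculation was possible. There is no stated figure to reproduce. Assumptions: 10%, 20% or 30% of 300 have diabetes (n = 30, 60, 90); two-sided alpha 0.05; power 80%; correlation 0.7 between values before and after illness; groups treated as independent; normal approximation.

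- Comparison with r register comparators per person: (1.960 + 0.842) × sqrt(1/n + 1/(rn)). For n = 60 and r = 4: 2.802 × sqrt(1/60 + 1/240) = 2.802 × 0.1443 = 0.40 SD.
- With the pre-illness value as covariate, multiply by sqrt(1 − 0.7²) = 0.714: 0.40 × 0.714 = 0.29 SD.
- Mean within-person change alone: 2.802 × sqrt(2 × (1 − 0.7)) / sqrt(n). For n = 60: 2.802 × 0.775 / 7.746 = 0.28 SD.

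| Detectable difference (SD) | n = 30 | n = 60 | n = 90 |
|---|---|---|---|
| 1:1 comparators | 0.72 | 0.51 | 0.42 |
| 1:4 comparators | 0.57 | 0.40 | 0.33 |
| 1:1, pre-illness covariate | 0.52 | 0.37 | 0.30 |
| 1:4, pre-illness covariate | 0.41 | 0.29 | 0.24 |
| Within-person change, no comparator | 0.40 | 0.28 | 0.23 |

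The last row is the precision for a change around the illness date. That change equals an effect of COVID-19 only if drift and calendar change are dealt with as well. Repeated pre-illness values help with drift; calendar change is better handled by a comparator indexed at the same dates.

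**The case against.** The best defence is that the schedule says when record follow-up is done, not which dates the extracted records may cover. Its columns are headed by time after discharge or illness, so a look-back has no column to appear in. The SCI-Diabetes clause in section 3.1 has no date limit, and neither does the content list in section 6.1. This stands in part: pre-illness values are unscheduled, not excluded. It does not supply a stated window, and it leaves the missing comparator untouched.

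The defence can add that the diabetes work is secondary, sits in a descriptive cohort, and is phrased as within the cohort or in affected patients. That limits the weight of the point, but the words effect and impact remain.

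It can also say that comparators would not deliver a clean causal estimate. Participants are consenting survivors, some from HDU or ICU, and people without recorded COVID-19 may include undiagnosed infections. That is correct. It is why comparators come second to the look-back in the fix, and why the descriptive wording is a legitimate alternative.

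Three stronger readings are tempting, but the document does not support them:

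- *A reader might infer that the same fault undermines the healthcare-use aim.* That objective is descriptive: "To determine long term healthcare resource utilisation in patients who have had COVID-19 disease". A cohort without a comparator can meet it.
- *A reader might infer that no record data exist for the first 6 months.* Notes and hospital systems supply admissions, readmissions, events and blood tests (sections 3.1 and 6.1). What the stated linkage leaves out is primary care contact before 6 months.
- *A reader might set section 3.5, "Any surplus tissue will be retained for future ethically approved research for up to 10 years", against the 25-year horizon and infer that biomarker links in years 11 to 25 are lost.* The limit applies to surplus tissue. A result assayed within 10 years can still be linked to a later outcome.

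**Conclusion.** The point holds for the diabetes aim, and only there. As written, the protocol asks for an effect of COVID-19 that its stated data cannot identify at any sample size, because it names neither a pre-illness window nor people without the illness. A description of diabetes control and care after COVID-19 remains fully achievable.

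The conclusion rests on reading the section 3.3 schedule as the only timing given for SCI-Diabetes. If a look-back is intended, stating it would resolve the baseline half of the problem. The detectable differences of 0.57 to 0.33 SD (1:4) and 0.41 to 0.24 SD (1:4 with a pre-illness covariate) depend on an assumed diabetes share and, for the second range, an assumed correlation. They show what a contrast might offer and are not shortfalls in the plan.

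The stated coverage of SCI-Diabetes supports drawing comparators from it. That it holds pre-illness values for participants is a reasonable inference from its being a shared routine record; the protocol does not say so.

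**What to change.** 1. Amend section 3.1 and the section 3.3 schedule so that SCI-Diabetes extraction covers a fixed look-back before the illness (for example 2 years, subject to the register holding those values), the first 6 months after it, and the follow-up already planned.
2. Make within-person change around the illness date the main diabetes analysis, using repeated pre-illness values to account for existing drift.
3. Where governance allows, add de-identified register comparators without recorded COVID-19, given the same calendar index date. Matching details can go in the analysis plan. Report residual confounding by severity, frailty and selection, and possible undiagnosed infection, as limits.
4. If neither the look-back nor comparators are obtained, replace effect and impact in the synopsis and in sections 2.1, 2.2 and 3.1 with a description of diabetes control and care after COVID-19.

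Items 1 to 3 cost a wider data request and its approval, with no added recruitment, visits or procedures. Item 4 costs an amendment to the wording.
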